9.2.3.4.3 Effect Modifiers

In this section, any factors (e.g., age at vaccination, chronic conditions, infections, concomitant vaccinations and medications) that are hypothesised to modify the effect of <<COVID-19 vaccine>> on the event of interest should be listed.

[Investigator should specify the effect modifiers and their operational definitions in this section].

9.3 Data Sources

The data sources for the exposures, events, and covariates will be listed in this section, including coding systems, data lag, and starting date of data availability. The size of the database and COVID-19 vaccination strategy should be included in this section. Validation data on relevant data elements should also be described.

9.4 Study Size

[figure not shown]
[To be completed by the study investigator(s) based on assumptions of number of cases and effect estimate size at the time of the full protocol development]

For signal evaluation studies sample size calculations should be conducted that would allow ability to detect risk with the highest precision. The sample size will be driven by the background rate of the event under evaluation and the size of the data source(s).

9.5 Data Collection and Management

This section assumes the approach of a distributed network of DAPs who agree to use a common protocol, common data model and common analytics. We recommend to prepare for a model where original data remain local, and are transformed in a common data model that will allow for study specific structural and semantic harmonization (model C, **Figure 6**) (Gini et al, 2020).

Figure 6. Options for multi-database studies in Europe

[If other models are used this section should be adapted]

In short, model C requires that each data access provider will extract the data required for the study and transform their local patient level data into a common data model (CDM). An example of a widely used common data model in Europe (currently 24 DAPs) is the ConcePTION CDM, which is publicly available². Extract, transform and load (ETL) design and instructions are available, as well as tools to check the quality of the data for the AESI listed above as these are also utilized for the ACCESS background rate protocol.

A common program to run quality checks, data transformation, and analysis should be prepared and verified and be sent to all DAPs. Aggregate results and summary estimates resulting from the programs should be returned to a single coordinating centre for pooled meta-analysis and reporting.

Routine procedures should include checking electronic files, maintaining security and data confidentiality, following analysis plans, and performing quality-control checks of all programs. Each partner should maintain any patient-identifying information securely on site according to internal standard operating procedures or guidance documents.

² <https://www.imi-conception.eu/wp-content/uploads/2020/10/ConcePTION-D7.5-Report-on-existing-common-data-models-and-proposals-for-ConcePTION.pdf>

Security processes should be in place to ensure the safety of all systems and data. Every effort should be made to ensure that data are kept secure so that they cannot be accessed by anyone except the study team.

Appropriate data storage and archiving procedures should be followed by each DAP and the coordinating organization, with periodic backups. Standard procedures should be in place at each research centre to restore files in the event of a hardware or software failure.

[Investigators should modify this section as needed for the specific study; if specific procedures of the identified research partners are known, they can be included here]

9.6 Data Analysis

9.6.1 Descriptive Analysis

Attrition diagrams demonstrating the loss of subjects applying inclusion and exclusion criteria should be provided.

For each study design, demographic characteristics of the study population (e.g. age at study entry, sex) and baseline characteristics (eg. co-morbidities) should be summarized for each data source using descriptive statistics. Description of <<COVID-19 vaccine>> type should be described and along with counts of exposure by calendar month to allow for inspection of time trends.

The distributions of the characteristics by study groups (index/comparison cohorts or cases/controls) should be presented in tables to demonstrate potential differences/or lack thereof between groups. For propensity matched cohorts the distribution and propensity scores should be plotted prior to the matching and balance after matching should be shown.

Counts and percentages should be presented for categorical variables (age at study entry in categories, sex, race/ethnicity, comorbidities). Mean, standard error, median and range should be presented for continuous variables (age at study entry). The missingness of variables should also be described.

Event counts should be provided categorized by level of severity/certainty. Appendices should provide code /algorithm counts for the events.

9.6.2 Measures of Association

Measures of association and statistical methods for each of the signal evaluation study designs are presented in **Table 4** below.

Null hypothesis for the study will be:

- **Cohort:** H_0 : the incidence of << event >> in the index group is equal to the incidence of << event >> in the comparison group.

- **Case-Control:** H_0 : the odds of cases exposed to <<COVID-19 vaccine >> is equal to the odds of controls exposed to <<COVID-19 vaccine>>.
- **Self-controlled:** H_0 : the incidence of << event>> in the risk period is equal to the incidence of << event>> in the control period.

Table 4. Measures of association according to the type of study design

Study design	Events	Statistical method	Measures of association
Cohort	All events excluding pregnancy outcomes	Poisson regression or Cox regression (time-dependent covariates/exposure)	Rate ratio or Hazard ratio
	Pregnancy outcomes	Binomial or logistic regression	Prevalence or odds ratio
Case-Control/Case cross over	All	Conditional logistic regression	Odds ratio
Self-controlled	All	Conditional Poisson regression	Incidence Rate Ratio

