9.1.1 Cohort

Retrospective (multi)-database cohort study where index <<COVID-19 vaccinated>> subjects and reference (subjects not vaccinated with << COVID-19 vaccine>>: reference cohort) are compared for occurrence of << event>>.

The comparison cohort will be matched using as example frequency matching or propensity score matching for important covariates such as age, sex and comorbidities (including COVID-19 infection prior to reference date) and markers of health care utilization (Austin, 2011). The comparison cohort could be the following:

- A concurrent comparison cohort including subjects not vaccinated with <<COVID-19 vaccine>> at the time of study start, identified at the same date (+/- 7 days – eg. anchored on a healthcare visit or pharmacy dispensing) of the exposure date (1st vaccine dose in case of multi-dose vaccine) of the matched vaccinated subjects. This calendar date time matching will allow to control for the variation in the SARS-CoV2 circulation and will minimize the risk of immortal time bias given that the time period before vaccination is immortal. To test for the presence and magnitude of immortal time, the time

difference between cohort entry and the date of start of vaccine distribution should be calculated for each cohort member and the frequency distribution of immortal time compared between the vaccinated and unvaccinated cohorts.

- If <<COVID-19 vaccine>> is distributed concurrently with the seasonal influenza vaccine, persons receiving both <<COVID-19 vaccine>> and the seasonal influenza vaccine could be compared with those receiving the influenza vaccine alone.
- A comparison cohort including subjects vaccinated with alternative <<COVID-19 vaccine>> in the same week as the matched index subjects. This time matching will allow to control for the variation in the SARS-CoV2 circulation.
- In the instance where the risk period of <<event>> is well known, the comparison cohort may be the same persons as the index cohort, with the comparison person time chosen after the ending of the risk window. Time trends in events cannot be controlled for in this manner.

[figure not shown]
The incidence rate ratio of the <<event>> is calculated comparing the incidence rate in index with that in the comparison cohort. The required follow-up time will depend on the event under evaluation, this follow-up time should take into account the vaccination schedule (**Figure 1**).

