9.1.2 Matched case-control

[figure not shown]
Retrospective (multi)-database case-control study where COVID-19 vaccination status is compared between cases (subjects who experienced << event>>) and controls (subjects who did not experience << event>>) in a specific time window.

Cases and controls should be matched on strong risk factors for the event and we recommend at least: age (year of birth), sex, and database (in case of multiple databases used) as well as calendar time. Controls should arise from a population where prior probability of exposure is the same as for the cases and be eligible to become and observed as a case if they develop the event of interest at a later date. As such persons may serve as control prior to becoming a case and may serve as a control for multiple cases (Richardson, 2004).

Index date for cases should be the disease date (preferably date of onset or first symptoms, otherwise diagnosis), the index date for the controls should be the index date of the corresponding cases. The calendar time matching, controls for confounding due to time related issues (e.g. circulation of SARS-Cov-2). Controls should be sampled using incidence density sampling (Lubin, 1984). For each subject in the database the start and end of follow-up is calculated, exclusion criteria are applied to all subjects and upon occurrence of an exclusion criterion, the follow-up time is censored. For each case, controls subjects who are actively registered in the data source at the index date of the case can be sampled or all eligible controls may be used (recommended if stratified analysis are conducted) (**Figure 2**).

In a case-control study, the aim is to compare the exposure during a specific time window between cases and controls. The time window prior to index date should be disease-specific plus the latency time period for the event under evaluation (e.g. for long latency events). For events with long latency, the risk window should be shortened or divided in small intervals to be able to assess the pattern of risk across different time windows. General recommendations are to have a time window of at least 2 months for events with short latency, and 3 years for events with long latency.

Figure 2. Case-control design

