9.2.2 Study Period, Population and Follow-up Period

The study population will comprise all persons in the source population that are eligible for the study according to specific inclusion and exclusion criteria (such as study period, design requirements and exclusion of prior events, see generic conditions in **Table 3**).

Eligible individuals should be identified in each of the database using a pre-specified selection process and/or by applying pre-specified algorithms. Attrition diagrams should be made. Follow-up time should start at the moment that the latest of the inclusion criteria is met, follow-up ends at the earliest of the occurrence of censoring conditions or the last data draw down/data availability.

Study period, study population and follow-up period for signal evaluation study designs are summarized in **Table 3**.

Note to future investigators: this section provides general information and should be adapted according to the type of safety study conducted.

Table 3. Study period, study population, and follow-up period by study design

Study design/Analysis Method	Study period	Study population [§]	Follow-up period
Cohort	Index cohort: from <<COVID-19 vaccine>> introduction until last data collected Comparison cohort: from <<COVID-19 vaccine>> introduction until last data collected	Index: all subjects who received at least 1-dose of COVID-19 vaccine Comparison: all subjects matched for covariates such as age, sex, comorbidities, identified from same data source(s) who did not receive COVID-19 vaccine or alternative vaccine.	Start: latest of fulfillment of inclusion criteria or start of study period End: earliest of end of study period or censoring conditions
Case-control	From <<COVID-19 vaccine>> introduction until date protocol is implemented or data is available	Cases: Subjects with a diagnosis of << event>> in the study period. Controls: Subjects matched on age, sex, database and/or region without << event>> diagnosis at the time of index	From start of follow-up until index date The length of risk period ('look back period') should be defined according to the event under evaluation

		date. Index date = index date of the corresponding cases	
SCCS	From <<COVID-19 vaccine>> introduction until latest data available	Subject who received at least 1-dose of COVID-19 vaccine and who experienced <<event>>	Start: latest of fulfillment of inclusion criteria or start of study period End: earliest of end of study period or censoring conditions

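### For pregnancy outcomes that depend on gestational time, Table 4 drops time-dependent exposure and the protocol never aligns the compared groups on gestational age, so the estimate is open to bias in either direction

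*Protocol*

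**What the plan says.** Protocol section 9.6.2, Table 4, splits the cohort design into two rows. The first, headed "All events excluding pregnancy outcomes", is given "Poisson regression or Cox regression (time-dependent covariates/exposure"). The second, pregnancy outcomes, is given "Binomial or logistic regression", reported as "Prevalence or odds ratio". Time-dependent exposure is mentioned only in the first row.

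Section 9.1.1 lists several possible comparators. The concurrent unvaccinated group is identified within 7 days "of the exposure date (1st vaccine dose in case of multi-dose vaccine) of the matched vaccinated subjects", and the protocol says that this "will minimize the risk of immortal time bias given that the time period before vaccination is immortal". It adds a check: the time from the start of vaccine distribution to cohort entry is compared between the cohorts.

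Table 3 (section 9.2.2) describes the cohort comparators as matched subjects "who did not receive COVID-19 vaccine or alternative vaccine", with no time reference. Its footnote says the population for pregnancy outcomes should be adapted to pregnant women. It does not adapt follow-up or the index date.

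For the case-control design, section 9.1.2 recommends matching at least on "age (year of birth), sex, and database (in case of multiple databases used) as well as calendar time", with incidence density sampling.

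Section 9.8 recognises that unvaccinated subjects may be vaccinated during the study and refers to censoring.

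**The concern.** Spontaneous abortion, stillbirth and preterm birth happen at a gestational age, and a pregnancy must still be ongoing at a given week to be vaccinated in that week. Pre-eclampsia, gestational diabetes and maternal death share this feature. A comparison of vaccinated with unvaccinated pregnancies is fair only if both groups start at the same gestational age, or if vaccination enters the model as a time-dependent exposure on that scale. Table 4 withholds the second route for exactly these outcomes, and nothing in the protocol requires the first.

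The row matters because it is the default. Table 2 marks the three self-controlled and case-crossover designs as unsuitable for all 12 pregnancy outcomes, and Annex 3 recommends a cohort analysis when the data already sit in electronic databases. Section 9.5 has every database run common programs, so a misalignment would be repeated in each of them. Pooling under section 9.6.3 would not remove it. The result could be false reassurance or a false alarm about a vaccine in pregnancy.

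**Working it through.** The protocol states no event rate, uptake or bias figure on this point, so there is no figure of its own to reproduce. The check uses a weekly gestational life table in which the vaccine has no effect, so an unbiased method returns 1.00.

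**Inputs, all assumed.** Spontaneous abortion risk is 10 to 20% over weeks 6 to 19, front-loaded. Preterm birth risk is 6 to 10% over weeks 24 to 36, back-loaded, among pregnancies followed from week 20. Weekly vaccination probability is 1% or 3%. It is constant, or varies: for spontaneous abortion only from week 12, or four times higher before week 12; for preterm birth four times higher from week 28.

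**Formulas.** Let R(g) be the remaining risk of the outcome in a pregnancy ongoing at week g, U(g) the number still pregnant and unvaccinated, and v(g) the uptake in that week.

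- Date anchoring without gestational matching: p1 = Σ U(g)v(g)R(g) / Σ U(g)v(g) and p0 = Σ U(g)R(g) / Σ U(g).
- Odds ratio: OR = [p1/(1 − p1)] / [p0/(1 − p0)].
- If v(g) is constant it cancels, so p1 = p0 and OR = 1. If v(g) varies with g, the two groups have different gestational ages at index and OR departs from 1 in a direction set by v(g).
- Matching on date and gestational week compares R(g) with R(g), so OR = 1. Time-dependent vaccination on the gestational scale also gives 1.

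**Examples of the ever/never arithmetic.**

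- Spontaneous abortion 20%, constant 3% uptake: p1 = 0.039, p0 = 0.393; OR = (0.039/0.961)/(0.393/0.607) = 0.0406/0.6474 = 0.063.
- Preterm birth 10%, base uptake 3%, heavier from week 28: p1 = 0.078, p0 = 0.195; OR = (0.078/0.922)/(0.195/0.805) = 0.0846/0.2422 = 0.35.

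**Null odds ratios over the assumed ranges.**

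| Outcome and uptake | Ever/never | Date anchor only | Date and gestational week, or time-dependent |
|---|---|---|---|
| Spontaneous abortion, constant | 0.06–0.10 | 1.00 | 1.00 |
| Spontaneous abortion, from week 12 only | 0.01–0.02 | 0.18–0.19 | 1.00 |
| Spontaneous abortion, four-fold before week 12 | 0.12–0.21 | 1.99–2.24 | 1.00 |
| Preterm birth, constant | 0.64–0.69 | 1.00 | 1.00 |
| Preterm birth, four-fold from week 28 | 0.35–0.52 | 0.84–0.87 | 1.00 |
| Preterm birth, doses before week 37 only (both uptake patterns) | 0.56–0.83 | 0.98–1.17 | 1.00 |

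In one further run (preterm risk 8%, 3% weekly uptake, all doses before week 24) ever/never gives 1.00 and the date anchor alone gives 1.39.

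In the spontaneous abortion runs doses count beyond week 19: at 1% a week, 14 weeks of uptake would vaccinate only 1 − 0.99^14 = 0.13, whereas the constant-uptake run with 10% risk vaccinates 0.27. Restricting index dates to weeks 6 to 19 would change the values, but they equal 1 in general only if uptake does not vary with week.

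**The immortal-time check.** It measures cohort entry against the start of vaccine distribution. Groups anchored within 7 days of each other agree on that almost by construction, whatever their gestational ages.

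**Case-control matching.** Take a miscarriage case at week 8 and a control at week 18, both still at risk, with constant 3% uptake from week 6. Chance of prior vaccination: 1 − 0.97^2 = 0.059 for the case and 1 − 0.97^12 = 0.306 for the control. Exposure odds ratio for the pair: (0.059/0.941)/(0.306/0.694) = 0.14. Reversing the two weeks gives its inverse, about 7. This shows that calendar matching does not equalise the opportunity to be vaccinated. It is not an estimate of the net bias.

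**The case against.** A reader might infer that Table 4 builds in immortal-time bias and makes the vaccine look protective. The documents do not support that. Table 4 names a regression model and never defines exposure as ever/never vaccinated. Section 9.1.1 anchors the concurrent comparator on the vaccination date precisely to limit immortal time, and with constant uptake that anchor gives 1.00. With other uptake patterns the bias can run either way. A logistic model with comparators matched on gestational week is unbiased under the null. Where the comparator received an alternative COVID-19 vaccine, both groups must reach a vaccination, so the mechanism does not apply in the same form.

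A reader might also picture a miscarriage case at week 10 matched to a control at week 30. Section 9.1.2 rules that out, because controls must be able to become cases, and its matching list is a minimum. Nor does the point cover the whole row: for anomalies and microcephaly a prevalence ratio with a closed exposure window can be reasonable.

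Finally, this is a template that tells investigators to adapt the population, risk windows and confounders.

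These points settle the direction and the scope, but not the gap. The date anchor is one of several comparators that may be chosen, and it aligns calendar time only. The adaptation note reaches the population alone. The choice of model by outcome is stated, not left open, and a plain binary model cannot censor the later vaccination that section 9.8 anticipates. Dropping comparators vaccinated later would move the analysis towards ever/never; keeping them as unvaccinated would dilute a real effect.

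**Conclusion.** The point holds for outcomes whose risk depends on gestational time: spontaneous abortion, stillbirth and preterm birth, and by the same reasoning pre-eclampsia, gestational diabetes and maternal death. Only spontaneous abortion and preterm birth were calculated. For these outcomes Table 4 withholds the time-dependent methods given to all other events, and no section aligns gestational age or deals with comparators vaccinated later in pregnancy.

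The bias comes from time zero and the exposure definition, not from the logistic model. It can be absent, protective or harmful: for spontaneous abortion under date anchoring, a null odds ratio of 1.00, about 0.2 or about 2 according to how uptake varies with gestational week. An ever/never definition would give 0.01 to 0.21. These values rest wholly on assumed risks and uptake. They show that the bias can be large, and they do not predict its size in any actual study.

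**What to change.** In Table 4, split the pregnancy row.

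- **Outcomes that depend on gestational time** (spontaneous abortion, stillbirth, preterm birth, pre-eclampsia, gestational diabetes, maternal death): Cox or Poisson regression on the gestational-age scale, with delayed entry at the first record of pregnancy and vaccination as a time-dependent exposure. Alternatively, keep the binary model only with comparators matched on gestational week at the index date, a defined exposure window (ending at 37 completed weeks for preterm birth) and a stated rule for comparators vaccinated later.
- **Outcomes fixed at birth** (major congenital anomalies, microcephaly): keep binomial or logistic models, with exposure defined in the relevant gestational window.

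For pregnancy outcomes, add gestational age at the index date to the matching factors in sections 9.1.1 and 9.1.2.

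The cost is a few lines of text and a requirement for pregnancy start dates. Preterm birth and fetal growth restriction already need these dates to be defined. Databases without pregnancy dating would drop out of these analyses, with some loss of precision.

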9.6.3 Data Integration

Results should be presented separately for each data source and pooled across data sources. The method for pooling of results will depend on the data-sharing policies of each of the participating data sources (see **Section 9.4**). We recommend for multi-site studies that aggregated data is shared and pooled. (Yoshida, 2018; Li, 2018; Shu, 2019).

If database access providers do not allow the necessary aggregate data to be shared, then data analysis will be performed by DAPs at their sites. Counts and coefficients would be shared with the study coordinating centre, and overall results would be summarised using meta-analytic techniques, such hybrid approaches were utilized previously to analyse narcolepsy data for the pandemic vaccine (Weibel, 2018).

Meta-analysis will be conducted using standard methods: heterogeneity should be tested and Forest plots be provided. Because of the size of data-sources we recommend random effect models (DerSimonian and Laird, 1986).

